1.3.4. Pharmacokinetics of GSK2879552 in Humans

GSK2879552 pharmacokinetics (PK) will be evaluated in a limited number of subjects in the first time in human study in small cell lung cancer patients (GSK study 200858, NCT# 02034123) prior to the initiation of this study. PK of GSK2879552 in human were predicted using in vitro microsomes and hepatocytes data, as well as in vivo intravenous (IV) pharmacokinetic data from mice, rats, and dogs combined with simple allometric scaling and Dedrick transformation. The human blood clearance is predicted to be around 5.4 mL/min/kg for a 70 kg human. The human blood volume of distribution is predicted to be most likely between 1.0 and 1.5 L/kg leading to a range of terminal half-life of 2.1 to 3.2 hours. Based on the good oral bioavailability in animals and the predicted low human clearance, the oral bioavailability is expected to be around 75% to 100% in humans.

As of 20-NOV-2015, the PK of GSK2879552 was evaluated following administration of single (N=18) and repeated (N=16) oral administration of 0.25 mg to 3 mg of GSK2879552 in subjects with SCLC in Study 200858 and following single (N=11) and repeated (N=8) oral administration of 1 mg to 8 mg in subjects with AML in Study 200200. GSK2879552 pharmacokinetics are characterized by a rapid absorption with

maximum concentration occurring typically within the first hour after dosing. GSK2879552 is eliminated slowly with an average terminal phase half-life of 12 to 38 hours, leading to a moderate average increase in exposure of 72% for AUC at 2 mg daily. Following single and repeated administration of 0.25 mg to 4 mg of GSK2879552, C_{max} and AUC tended to increase in a dose proportional fashion.

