1.3.5. Clinical Safety of GSK2879552

Summary of findings from clinical studies conducted with GSK2879552 can be found in the Investigator Brochure for GSK2879552 [GlaxoSmithKline Document Number [2013N168888_03](#)].

As of 20-NOV-2015, 11 subjects have been enrolled in Part 1 at once daily doses of 1 mg (n=1), 2 mg (n=2), 4 mg (n=7), and 8 mg (n=1). All 11 subjects (100%) had experienced AEs. The most frequently reported AEs (>20%) were fatigue, febrile neutropenia, nausea, anemia, decreased appetite, hypotension, rash, cellulitis, hypokalemia, and local edema. All Grade 4 AEs were hematological and included thrombocytopenia and neutropenia. Treatment-related AEs reported in at least 10% of subjects were nausea, decreased appetite, and thrombocytopenia. The treatment-related thrombocytopenia AEs were Grade 4 in both subjects; one of these subjects also had Grade 3 febrile neutropenia and Grade 3 anemia. Other treatment-related events that were Grade 3 or 4 included anemia and nausea. There were no fatal AEs.

All 11 subjects in Study 200200 have experienced SAEs. The most common SAE was febrile neutropenia. All cases of febrile neutropenia resolved. No other SAEs occurred in more than 1 subject. One subject had fatal pleural effusion secondary to disease under study, which was considered by the investigator to be not related to study treatment.

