### 9.1.3. Statistical Analyses / Methods

Details of the planned displays are provided in [Appendix 10](#): List of Data Displays and will be based on GSK Data Standards and statistical principles.

Unless otherwise specified, endpoints / variables defined in Section 9.1.1 will be summarised using descriptive statistics, graphically presented (where appropriate) and listed.

Plasma concentration-time data for GSK2879552 and ATRA will be listed by dose and Plasma concentration-time data for GSK2879552 will be summarized using descriptive statistics (n, mean, standard deviation [SD], median, minimum and maximum) by planned relative assessment time. Mean and/ or median values will be plotted over time. Individual plasma and urinary (if available) PK parameters values as well as a descriptive summary (mean, standard deviation, median, minimum, maximum, geometric mean, and the standard deviation, Coefficient of variance [CV]% and 95% confidence interval of log-transformed parameters, if applicable) by dose cohort will be reported. The following pharmacokinetic statistical analyses will only be performed, if sufficient data is available.

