#### 9.1.3.2. Accumulation

If data permits, accumulation using ANOVA will be performed for AUC(0- $\tau$ ) on Day 15 vs AUC(0- $\tau$ ) on Day 1 by dose cohort.

To estimate the extent of accumulation after repeat dosing, the observed accumulation ratio (Ro) based on AUC data will be determined as follows:

$$Ro = AUC(0-\tau)_{D15} / AUC(0-\tau)_{D1}$$

Assuming both linear and time-invariant pharmacokinetics, the Ro at steady-state should be unity.

An ANOVA with a random effect term for subject and fixed effect terms for day will be performed by dose on the  $\log_e$ -transformed PK parameters AUC(0- $\tau$ ). Day will be treated as a class variable in the model. The accumulation ratio of GSK2879552 will be estimated by calculating the ratio of the geometric least squares (GLS) means of the PK parameter between Day 15 and Day 1 for all dose levels and the corresponding 90% CI for each ratio.

The accumulation ratio will be summarized by dose.

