#### 9.1.3.3. Time Invariance

To evaluate whether the pharmacokinetics remains unaltered after repeat dosing a similar analysis to that described above will be carried out after  $\log_e$ -transformation of AUC(0- $\infty$ ) for D1 and AUC(0- $\tau$ ) for D15, the difference of which provides the steady-state ratio (Rs).

A mixed effect model will be fitted with day as a fixed effect and subject as a random effect for each treatment (dose) separately. AUC(0- $\tau$ ) on D15 will be compared to AUC(0- $\infty$ ) on D1 in order to assess time invariance for each dose. The Kenward & Roger (KR) degrees of freedom approach will be used. The ratio and 90% confidence interval will be calculated by back-transforming the difference between the least square means for the two days and associated 90% confidence interval, for each dose. Assuming both linear and time-invariant pharmacokinetics, the Rs at steady-state should be one.

The time invariance ratio will be summarized by dose.

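### Accumulation and time invariance are modelled dose by dose, which gives no confidence interval at one-subject doses and an uninformative one at two; a single model with a dose-by-day term would use the same data better

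*SAP*

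**What the plan says.** SAP 9.1.3.2 specifies for accumulation: "An ANOVA with a random effect term for subject and fixed effect terms for day will be performed by dose". The response is log AUC(0-τ), and the output is the Day 15 to Day 1 ratio with "the corresponding 90% CI for each ratio". SAP 9.1.3.3 specifies for time invariance: "A mixed effect model will be fitted with day as a fixed effect and subject as a random effect for each treatment (dose) separately", with Kenward-Roger degrees of freedom and again a 90% interval per dose. Tables 4.5 and 4.6 (SAP 11.10.7) carry the results. The PK_T2 shell in SAP Appendix 11 shows rows for 1 mg and 2 mg, each with an interval column.

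The analyses are conditional. SAP 9.1.3 says "The following pharmacokinetic statistical analyses will only be performed, if sufficient data is available", and 9.1.3.2 opens with "If data permits, accumulation using ANOVA will be performed for". Neither section sets a minimum number of subjects or names a fallback.

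On numbers, Protocol 1.3.5 gives the position at 20-NOV-2015: "once daily doses of 1 mg (n=1), 2 mg (n=2), 4 mg (n=7), and 8 mg (n=1". For the same date Protocol 1.3.4 reports "repeated (N=8) oral administration of 1 mg to 8 mg in subjects with AML in Study 200200". SAP 5.1 lists eight reporting groups without a count for any of them.

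**The concern.** Small dose groups follow from the design. Protocol 4.2.1 escalates monotherapy with one subject per cohort until a toxicity trigger, then with at least two. A day-plus-subject model fitted to one subject leaves nothing from which to estimate residual variance. Fitted to two subjects, it leaves a single degree of freedom. Separate fits also discard what the other doses say about within-subject variability.

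Accumulation ratio and time invariance are named among the Part 1 secondary PK endpoints (Protocol Section 2, SAP 2.2). At stake is whether the sparse doses get an interval that can be interpreted. Because adequacy of the data is left undefined, which doses get one would be settled after the data are seen.

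**Working it through.** The plan states no precision for these ratios, so there is no figure to reproduce.

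**Inputs from the documents**
- Enrolled by dose at 20-NOV-2015: 1, 2, 7, 1 at 1, 2, 4, 8 mg; total 11 (Protocol 1.3.5).
- AML subjects with repeat-dose PK at that date: 8 (Protocol 1.3.4).
- Interval level 90% (SAP 9.1.3.2 and 9.1.3.3).

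**Assumptions**
- The eight subjects form complete Day 1/Day 15 pairs split 1/2/4/1. The dose-limiting toxicity denominators in Protocol 13.2, Table 6 are 1, 2, 4 and 1 and also sum to 8, but the documents do not say these are the same subjects.
- Within-subject SD of log AUC is 0.3, range 0.2 to 0.4. The documents give no value.

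**Formulas**
- CI factor = exp(t(0.95, df) × SD × √2 / √n), where n is the number of pairs at the dose. The interval is the ratio divided by, and multiplied by, this factor.
- Separate model: df = n − 1.
- One model with dose, day, dose-by-day and subject: df = pairs minus doses = 8 − 4 = 4, so t = 2.132.

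**Worked case, n=2, SD 0.3** (√2/√2 = 1)
- Separate: exp(6.314 × 0.3) = exp(1.894) = 6.65.
- Pooled: exp(2.132 × 0.3) = exp(0.640) = 1.90.

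| n at dose | Model | df | t | SD 0.2 | SD 0.3 | SD 0.4 |
|---|---|---|---|---|---|---|
| 1 | separate | 0 | – | none | none | none |
| 1 | pooled | 4 | 2.132 | 1.83 | 2.47 | 3.34 |
| 2 | separate | 1 | 6.314 | 3.54 | 6.65 | 12.5 |
| 2 | pooled | 4 | 2.132 | 1.53 | 1.90 | 2.35 |
| 4 | separate | 3 | 2.353 | 1.39 | 1.65 | 1.95 |
| 4 | pooled | 4 | 2.132 | 1.35 | 1.57 | 1.83 |

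**Illustration.** Protocol 1.3.4 cites an average AUC increase of 72% at 2 mg daily, a ratio of 1.72. With two subjects and SD 0.3, the separate interval runs from 1.72/6.65 = 0.26 to 1.72 × 6.65 = 11.4. The pooled interval runs from 1.72/1.90 = 0.91 to 1.72 × 1.90 = 3.27. The pooled interval is usable, though not tight.

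**One day effect for all doses.** With 8 pairs, df = 7 and t = 1.895, so the factor is exp(1.895 × 0.3 × √2/√8) = exp(0.284) = 1.33 (1.21 at SD 0.2, 1.46 at SD 0.4). This is the narrowest interval, but it is one ratio for every dose and assumes accumulation does not depend on dose.

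**The case against.** A reader might infer that most doses will lack a usable interval. That is true of the 2015 snapshot (three of four doses) but not shown for the SAP's eight groups. The SAP follows Amendment 5 of October 2017 and includes 12 mg, 20 mg, a 20 mg PK/PD expansion and a 2 mg plus ATRA group, all without counts. Combination cohorts plan three or more subjects (Protocol 4.2.2), and any level may be expanded to 12 (Protocol 4.2.3). The 4 mg dose already had seven enrolled. The highest cleared dose at that date was 4 mg (Protocol 1.4.4.2), so more subjects at 8 mg are plausible. This part of the objection stands.

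A reader might also infer that the endpoints cannot be estimated. They can: a single subject still yields an observed ratio, individual PK parameters are listed, and both ratios are summarised by dose (SAP 9.1.1.2, 9.1.3). What is missing is the interval.

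The plan also anticipates sparse data by making these analyses conditional, and withholding a model-based interval at n=1 is defensible. That stands too, but a condition with no threshold does not say what happens at n=2, and dropping sparse doses wastes their contribution.

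Finally, the study was terminated, the report is abbreviated and the analysis is descriptive (SAP 2.1, 2.4), so no decision rests on these intervals. That limits the importance of the point, not its correctness.

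**Conclusion.** The point holds as a modest improvement to the analysis of a secondary endpoint. On the only documented counts, separate models give no interval at 1 mg and 8 mg and a 90% interval at 2 mg whose upper limit is about 44 times its lower (6.65² at SD 0.3). Pooling the residual variance reduces that span to about 3.6 times (1.90²). It gives one-subject doses an interval of about times or divided by 2.47, which remains weak and rests wholly on variance seen at other doses. At n=4 the gain is small (1.65 to 1.57).

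The degrees of freedom at each documented count follow from the models, given complete pairs. The sizes rest on the assumed 1/2/4/1 split and the assumed SD. The documents do not establish how many of the eight groups are affected. They also do not support a common ratio as the main result: dose proportionality is described only for 0.25 to 4 mg (Protocol 1.3.4), while the groups run to 20 mg.

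**What to change.** In SAP 9.1.3.2 and 9.1.3.3, replace the by-dose fits with one mixed model per endpoint on log AUC over all groups: fixed effects for dose, day and dose-by-day, and a random subject effect. Make 2 mg plus ATRA its own level, and say whether 20 mg and 20 mg PK/PD expansion are one level or two. Take each dose's ratio and 90% interval from this model. The dose-by-day term keeps each ratio specific to its dose.

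In Tables 4.5 and 4.6, flag any dose with one subject as having an interval based on variance borrowed from other doses. A single overall day ratio may be added as supportive only, with its assumption of equal accumulation at all doses stated.

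The cost is a few lines of SAP text and code, with no new data. The one downside is the assumption of a common within-subject variance across doses, to be checked with residual plots by dose.

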#### 9.1.3.3. Time Invariance

To evaluate whether the pharmacokinetics remains unaltered after repeat dosing a similar analysis to that described above will be carried out after  $\log_e$ -transformation of AUC(0- $\infty$ ) for D1 and AUC(0- $\tau$ ) for D15, the difference of which provides the steady-state ratio (Rs).

A mixed effect model will be fitted with day as a fixed effect and subject as a random effect for each treatment (dose) separately. AUC(0- $\tau$ ) on D15 will be compared to AUC(0- $\infty$ ) on D1 in order to assess time invariance for each dose. The Kenward & Roger (KR) degrees of freedom approach will be used. The ratio and 90% confidence interval will be calculated by back-transforming the difference between the least square means for the two days and associated 90% confidence interval, for each dose. Assuming both linear and time-invariant pharmacokinetics, the Rs at steady-state should be one.

The time invariance ratio will be summarized by dose.

## **11. APPENDICES**

### **11.1. Appendix 1: Protocol Deviation Management and Definitions for Per Protocol Population**

#### **11.1.1. Exclusions from Per Protocol Population**

There will be no Per Protocol population used for any displays or statistical analysis.

**11.2. Appendix 2: Schedule of Activities**

**11.2.1. Protocol Defined Schedule of Events**

Refer to Protocol Amendment 5 Section 7.1.

**11.3. Appendix 3: Assessment Windows**

No assessment windows will be applied.

## 11.4. Appendix 4: Study Phases and Treatment Emergent Adverse Events

### 11.4.1. Study Phases

Assessments and events will be classified according to the time of occurrence relative to treatment start date.

Study Phase	Definition
Pre-Treatment	Date < Study Treatment Start Date
On-Treatment	Study Treatment Start Date ≤ Date ≤ Study Treatment Stop Date
Post-Treatment	Date > Study Treatment Stop Date

#### 11.4.1.1. Study Phases for Concomitant Medication

Study Phase	Definition
Prior	If medication end date is not missing and is before 28 days prior to screening visit
Concomitant	Any medication that is not a prior

**NOTES:**

- Please refer to [Appendix 7: Reporting Standards for Missing Data](#) for handling of missing and partial dates for concomitant medication. Use the rules in this table if concomitant medication date is completely missing.

## 11.5. Appendix 5: Data Display Standards & Handling Conventions

### 11.5.1. Reporting Process

Software	

 
The currently supported versions of SAS software will be used.
 
	
Reporting Area	
HARP Server	: US1SALX00259
HARP Compound	: Compound: GSK2879552, Study:200200
Analysis Datasets	

 
Analysis datasets will be created according to Legacy GSK A&R dataset standards
 
	
Generation of RTF Files	

 
RTF files will be generated for tables and figures.
 
	

### 11.5.2. Reporting Standards

General	

 
The current GSK Integrated Data Standards Library (IDSL) will be applied for reporting, unless otherwise stated (IDSL Standards Location: https://spope.gsk.com/sites/IDSLLibrary/SitePages/Home.aspx):             
 
4.03 to 4.23: General Principles
 
5.01 to 5.08: Principles Related to Data Listings
 
6.01 to 6.11: Principles Related to Summary Tables
 
7.01 to 7.13: Principles Related to Graphics
 
 
 
	
Formats	

 
GSK IDSL Statistical Principles (5.03 & 6.06.3) for decimal places (DP's) will be adopted for reporting of data based on the raw data collected, unless otherwise stated.
 
Numeric data will be reported at the precision collected on the eCRF.
 
The reported precision from non eCRF sources will follow the IDSL statistical principles but may be adjusted to a clinically interpretable number of DP's.
 
	
Planned and Actual Time	

 
Reporting for tables, figures and formal statistical analyses:             
 
Planned time relative to dosing will be used in figures, summaries, statistical analyses and calculation of any derived parameters, unless otherwise stated.
 
The impact of any major deviation from the planned assessment times and/or scheduled visit days on the analyses and interpretation of the results will be assessed as appropriate.
 
 
 
Reporting for Data Listings:             
 
Planned and actual time relative to study drug dosing will be shown in listings (Refer to IDSL Statistical Principle 5.05.1).
 
Unscheduled or unplanned readings will be presented within the subject's listings.
 
Visits outside the protocol defined time-windows (i.e. recorded as protocol deviations) will be included in listings but omitted from figures, summaries and statistical analyses.
 
 
 
	
Unscheduled Visits	

 
Unscheduled visits will not be included in summary tables and figures.
 
	

 
All unscheduled visits will be included in listings
 
	
Descriptive Summary Statistics	
Continuous Data	Refer to IDSL Statistical Principle 6.06.1
Categorical Data	N, n, frequency, %
Graphical Displays	

 
Refer to IDSL Statistical Principals 7.01 to 7.13.
 
	

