7. STUDY ASSESSMENTS AND PROCEDURES

A signed, written informed consent form must be obtained from the subject prior to any study-specific procedures or assessments being performed.

The timing of each assessment is listed in the Time and Events Table (Section 7.1). The timing and number of the planned study assessments may be altered during the course of the study based on newly available data (e.g. to obtain data closer to the time of peak plasma concentrations) to ensure appropriate monitoring for the following assessments: safety, PK, PD/biomarker assessments. The change in timing or addition of time points for any of the planned study assessments listed above must be approved and documented by GSK, but this will not constitute a protocol amendment. The institutional review board (IRB) or ethics committee (EC) will be informed of any safety issues that require alteration of the safety monitoring scheme.

Whenever vital signs, 12-lead ECGs and blood draws are scheduled for the same nominal time, the assessments should occur in the following order: 12-lead ECGs, vital signs, blood draws.

If the blood draw is done first, there should be at least 15 minute interval before the vital signs and 12-lead ECGs measurements are taken.

On clinic days, study drug should be taken in the clinic after all the safety procedures (including CBC) and blood sampling for PK/PD, if applicable, are completed.

Detailed procedures for obtaining each assessment are provided in the Study Procedures Manual (SPM).

Visit Window

Informed consent should be signed within 35 days prior to dosing.

Baseline disease assessment should be completed within **21 days** prior to dosing start.

ECHO/MUGA should be completed within **35 days** prior to dosing start.

Pregnancy testing should be completed **7 days** prior to dosing start and all other screening assessments should be completed within **14 days** prior to dosing start.

Visits in the first 4 weeks will be allowed ± 1 day window. Bone marrow on Day 15 can be done between Day 8 and Day 21.

Visits beyond the first 4 weeks will have ± 3 days window.

The End of Treatment visit should be completed within **14 days** from the last dose.

Time Window for PK sampling

0.25, 0.5, 1 and 1.5 hours post dose sampling: ± 5 minutes

2, 3, 4 hours post dose sampling: ± 10 minutes

6, 8, and 10 hours post dose sampling: ± 30 minutes

24 hours post dose sampling: ± 1 hour and should be done before the next dose administration.

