Bone marrow aspirate/biopsy for disease assessment ^{24, 25}	X ²⁰					X ¹⁸						Wk 4, between Wk 6- 8 ¹⁹ , Wk 12 and then every 12 wks.			
Telephone call for survival status ²⁶														X	
PGX sample (buccal swab)	X														
PK blood sample on bone marrow day ¹⁵						X (bone marrow day)						Wk 4, between Wk 6- 8, Wk 12 and then every 12 wks			
Transfusion Assessment ¹³	X				X		X				X		Every week x 4 (wk 4-7), wk 8, then every 4 wks		

	SCR	First Treatment Phase (28 days)										Continuation Phase	EOT	SFU Q12W
		D 1	D 2	D 4	D 8	D 11	D 15	D 16	D 18	D22	D25			
Adverse Events		continuous												
Con Meds		continuous												
Highest Dose in PK/PD expansion cohort ONLY														
Blood for metabolite evaluation		X ⁹	X ⁹				X ⁹	X ⁹						
Urine for metabolite evaluation		X ^{5, 12}	X ⁵				X ⁵	X ⁵						
Urine for PK		X ^{5, 12}	X ⁵				X ⁵	X ⁵						

1. A blood sample will be collected for PK analysis on D1 at following time points: pre-dose, 0.25, 0.5, 1, 1.5, 2, 3, 4, 6, 8, 10, and 24 hrs post dose. In the combination cohort, a blood sample for ATRA PK analysis will be also collected at the same time points except for the 0.25, 10 and 24 hour sample. Additional samples may be collected at 48 and 72 hrs post dose in subjects not receiving a dose on Days 2 and 3 to better characterize the terminal half-life of GSK2879552, if needed.
2. A blood sample will be collected for PK analysis on D8 at following time points: pre-dose, 0.5, 3 hrs post dose. In the combination cohort, a blood sample for ATRA PK analysis will be also collected at the same time points.
3. A blood sample will be collected for PK analysis on D15 at following time points: pre-dose, 0.25, 0.5, 1, 1.5, 2, 3, 4, 6, 8, 10, and 24 hrs post dose. In the combination cohort, a blood sample for ATRA PK analysis will be also collected at the same time points except for the 0.25, 10 and 24 hour sample.
4. PK blood sample should be taken pre-dose around the same time as CBC. If the dose has been modified since the last PK sample and an unscheduled CBC sample is taken, a PK sample should be obtained together with the first unscheduled CBC sample. PK sample will not be collected beyond week 48.

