7.4. Pharmacokinetics

7.4.1. Blood Sample Collection for Pharmacokinetics

Blood samples for pharmacokinetic (PK) analysis of GSK2879552 and ATRA will be collected at the time points indicated in the Time and Events Schedule (Section 7.1). Additional blood samples will be collected for metabolic profiling in the highest dose cohort of the PK/PD expansion in Part 1 at the time points indicated in the Time and Events Schedule (Section 7.1)

Each PK sample should be collected as close as possible to the planned time relative to the dose (i.e., time zero) administered to the subject on PK days. The actual date and time of each blood sample collection will be recorded along with the date and time of the prior dose administration. The timing of PK samples may be altered and/or PK samples may be obtained at additional time points to ensure thorough PK monitoring. This would not require a protocol amendment.

Details on PK blood sample collection, processing, storage and shipping procedures are provided in the SPM.

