##### 9.1.1.2. Derived Pharmacokinetic Parameters

Pharmacokinetic analysis of GSK2879552 will be conducted by noncompartmental methods using WinNonlin (Version 6.3 or higher). However pharmacokinetic analysis of ATRA will not be conducted due to the sample size limitations. The following pharmacokinetic parameters will be determined for if data permit:

Parameter	Parameter Description
AUC(0-t)	Area under the concentration-time curve from time zero to the time of the last quantifiable concentration (C(t)) will be calculated using the linear trapezoidal rule for each incremental trapezoid and the log trapezoidal rule for each decremental trapezoid.
$AUC(0-\tau)$	Area under the concentration-time curve during a dosing interval of duration "tau".
AUC (0-∞)	Area under the concentration-time curve extrapolated to infinity will be calculated as: $AUC = AUC(0-t) + C(t) / \lambda_z$ This will be calculated for Day 1 only
C max	Maximum observed plasma concentration, determined directly from the concentration-time data.
t max	Time to reach C max , determined directly from the concentration-time data.
t 1/2	Apparent terminal half-life will be calculated as: $t_{1/2} = \ln 2 / \lambda_z$
λ z	Apparent terminal phase elimination rate constant
C T	Trough concentration

To estimate the extent of accumulation after repeat dosing, the observed accumulation ratio (Ro) may be determined from the ratio of AUC(0- $\tau$ ) in Day 15/ AUC(0- $\tau$ ) in Day 1. The ratio of AUC(0- $\tau$ ) on Day 15/ Day 1 AUC(0- $\infty$ ) will be calculated to assess time invariance.

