### 11.5.3. Reporting Standards for Pharmacokinetic

Pharmacokinetic Concentration Data	
PC Windows Non-Linear (WNL) File	PC WNL file (CSV format) for the non-compartmental analysis by Clinical Pharmacology Modelling and Simulation function will be created according to [Insert document name]. Note: Concentration values will be imputed as per GUI_51487
Descriptive Summary Statistics, Graphical Displays and Listings	Refer to IDSL PK Display Standards. Refer to IDSL Statistical Principle 6.06.1. Note: Concentration values will be imputed as per GUI_51487 for descriptive summary statistics/analysis and summarized graphical displays only.
Pharmacokinetic Parameter Data	
Is NQ impacted PK Parameters Rule Being Followed	Yes, refer to [Standards for Handling NQ Impacted PK Parameters].
Descriptive Summary Statistics, Graphical Displays and Listings	Refer to IDSL PK Display Standards. Refer to GUI_51487

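### The SAP's stated default is planned sampling time for derived parameters, with no visible exception for the non-compartmental PK parameters although actual times are recorded: a small, avoidable error

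*SAP*

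**What the plan says.** - **General rule.** SAP 11.5.2, for tables, figures and formal analyses: "Planned time relative to dosing will be used in figures, summaries, statistical analyses and calculation of any derived parameters, unless otherwise stated".
- **Role of actual time.** The same section gives it a place in listings: "Planned and actual time relative to study drug dosing will be shown in listings".
- **Parameter definitions.** SAP 9.1.1.2 carries the phrase Derived Pharmacokinetic Parameters in its title, so the general rule reaches it. It names method and software, "Pharmacokinetic analysis of GSK2879552 will be conducted by noncompartmental methods using WinNonlin (Version 6.3 or higher", but no time basis. Protocol 13.8.3.1 is silent too.
- **Input file.** SAP 11.5.3 says the concentration file for WinNonlin "will be created according to [Insert document name", followed by the closing bracket. The reference was never completed.
- **Outside guidance.** SAP 11.5.3 says "Concentration values will be imputed as per GUI_51487", and cites the same guide again for the summaries, displays and listings of PK parameters. The SAP reference list titles it as guidance on non-compartmental analysis.
- **What is collected.** Protocol 7.4.1: "The actual date and time of each blood sample collection will be recorded along with the date and time of the prior dose administration".

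**The concern.** A non-compartmental calculation uses the time axis directly: as interval widths for AUC, as the regressor for the terminal slope, and as tmax itself. Replacing the true time by the nominal one adds error that the recorded data would remove.

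Two features of this study make that worth attention. The late samples, which set the terminal slope, have the widest windows. And the last routine serial sample is at 24 h against a reported terminal half-life of 12 to 38 h (protocol 1.3.4), so AUC(0-∞) leans heavily on extrapolation. AUC(0-∞) on Day 1 feeds both the dose-proportionality model (SAP 9.1.3.1) and the time-invariance ratio fitted separately for each dose (SAP 9.1.3.3).

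PK of GSK2879552 is the first-listed secondary objective. Cohorts are small: at 20 November 2015 there were 1, 2, 7 and 1 subjects at 1, 2, 4 and 8 mg (protocol 1.3.5), so there is little averaging within a dose.

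**Working it through.** The documents give no figure that depends on the time basis, so there is nothing to reproduce. The check sizes the error by simulation.

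**Inputs from the protocol**
- Day 1 and Day 15 sampling (7.1): "pre-dose, 0.25, 0.5, 1, 1.5, 2, 3, 4, 6, 8, 10, and 24 hrs post dose".
- Windows (section 7): "0.25, 0.5, 1 and 1.5 hours post dose sampling: ± 5 minutes"; ±10 min at 2 to 4 h; ±30 min at 6 to 10 h; ±1 h at 24 h.
- Terminal half-life 12 to 38 h. The 72% rise in AUC at 2 mg daily implies an intermediate value: k = -ln(1 - 1/1.72)/24, so ln 2/k = 19.1 h.

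**Windows as a share of nominal time:** 5/15 = 33% at 0.25 h, 5/30 = 17% at 0.5 h, 5/60 = 8% at 1 h, 8% to 5% at 6 to 10 h, 4% at 24 h.

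**Assumptions.** Noise-free profiles C(t) = A·exp(-0.5t) + exp(-βt) - (A+1)·exp(-5t), with β = ln 2/half-life; A = 0 (one-compartment) or A = 2 (biexponential). Sampling times uniform within the windows. AUC by the SAP's rule, linear up and log down. Terminal slope from the last four points. Each profile is analysed twice, on planned and on actual times; 10,000 profiles per scenario (5,000 for AUC(0-t)).

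**95% range of planned relative to actual, per profile**

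| Half-life, model | Half-life | AUC(0-∞) | AUC(0-t) | AUC(0-τ), fixed 24 h |
|---|---|---|---|---|
| 12 h, one-comp. | -6.0% to +6.7% | -3.5% to +3.9% | -3.1% to +3.4% | ±1.6% |
| 12 h, biexp. | -6.0% to +6.8% | -3.0% to +3.3% | -2.8% to +3.0% | ±1.7% |
| 19.1 h, one-comp. | -6.0% to +6.8% | -4.2% to +4.7% | -3.3% to +3.6% | -1.1% to +1.2% |
| 19.1 h, biexp. | -6.0% to +6.8% | -3.6% to +4.1% | -2.9% to +3.1% | -1.3% to +1.4% |
| 38 h, one-comp. | -5.9% to +6.7% | -4.9% to +5.6% | -3.5% to +3.8% | ±0.7% |
| 38 h, biexp. | -6.0% to +7.0% | -4.5% to +5.2% | -3.2% to +3.4% | ±0.9% |

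The largest tmax difference is 5 min. Repeat runs agree, with AUC(0-τ) at most about ±1.8%. AUC(0-t) moves more than AUC(0-τ) because its endpoint shifts: 24 h on planned time, 23 to 25 h on actual time.

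**Systematic lateness.** If every sample is late by its full window: AUC(0-τ) -0.7% to -2.9%, AUC(0-∞) -3.3% to -4.0%, half-life -2.9% to -3.0%, tmax -5 min.

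**Why AUC(0-∞) is exposed.** Under one compartment the fraction extrapolated beyond 24 h is about exp(-ln 2 × 24/half-life): 25%, 42% and 65% at 12, 19.1 and 38 h.

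**Against subject variability.** The documents give no between-subject CV, so a range is assumed. Total SD inflates by √(CV² + s²)/CV - 1, with the largest simulated timing SDs s = 3.7% (half-life), 3.1% (AUC(0-∞)) and 0.9% (AUC(0-τ)):
- CV 15%: 3.0%, 2.1%, 0.2%.
- CV 20%: 1.7%, 1.2%, 0.1%.
- CV 40%: 0.4%, 0.3%, under 0.1%.

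**Effect on the power-model slope.** A 5% AUC error confined to one end of the 1 to 20 mg range moves the slope by about 0.05/ln(20) = 0.017.

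**The case against.** The strongest reply is that the rule is a general reporting default that yields to any contrary statement. The non-compartmental work is assigned to a separate clinical pharmacology function with its own input file (SAP 9.1, 11.5.3) and may be reported separately. GUI_51487 is by title guidance on exactly this analysis and is cited for parameter output as well as for imputation; it, or the unnamed file specification, may require actual times. This stands. A reader might infer that planned times will certainly be used in WinNonlin. The documents do not show that: they show a stated default, no visible exception and an incomplete reference.

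The second reply is that the effect is small. This also stands. The 33% at 0.25 h is a ratio of clock times at one early sample, not an error in any parameter. A figure near ±3% belongs to AUC(0-t), not to AUC over a fixed 24 h. The accumulation ratio, built on AUC(0-τ), is little affected. The analysis is descriptive and the study ended early with an abbreviated report.

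The third reply is mitigation: SAP 11.5.2 promises to assess the impact of major deviations from planned times, and listings show both times. That addresses gross departures, not routine in-window differences, and it does not alter the rule.

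**Conclusion.** The point holds as a minor one. The SAP states planned time for derived parameters and nothing visible exempts the non-compartmental parameters, although the better times are recorded. If an outside document already requires actual times, the SAP's stated default conflicts with it and should still be corrected.

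The sizes are those tabulated above. They assume uniform in-window sampling, a half-life of 12 to 38 h, an absorption rate of 5/h and a four-point terminal slope. Samples taken outside the windows would give larger errors. A reader might infer that the PK conclusions are unsafe; with errors of a few percent against any plausible subject variability, that is not supported.

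**What to change.** Add one sentence to SAP 9.1.1.2 or 11.5.3: all non-compartmental parameters are computed from actual elapsed time since dose. Keep planned times for concentration summaries and mean plots, where they are appropriate. Replace the placeholder in SAP 11.5.3 with the name of the file specification, and check that it and GUI_51487 agree with the new sentence.

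No new data are needed: the protocol already has both times recorded.
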